8.3.3 CLASSIFICATION OF AN ADVERSE EVENT

8.3.3.1 SEVERITY OF EVENT

For adverse events (AEs) the following guidelines will be used to describe severity.

- **Mild** – Events require minimal or no treatment and do not interfere in participant's daily activities or functioning.
- **Moderate** – Events result in a low level of inconvenience and may result in some interference in participant's daily activities or functioning.
- **Severe** – Events interrupt a participant's usual daily activity or functioning and may require systemic drug therapy or other treatment. Severe events are usually potentially life-threatening or incapacitating. Of note, the term "severe" does not necessarily equate to "serious."

8.3.3.2 RELATIONSHIP TO STUDY INTERVENTION/EXPERIMENTAL MANIPULATION

All adverse events (AEs) will have their relationship to study procedures, including the intervention, assessed by the student participant's treating counselor and/or IE based on the temporal relationship and his/her clinical judgment. The degree of certainty about causality will be graded using the categories below.

- **Definitely Related** – There is clear evidence to suggest a causal relationship, and other possible contributing factors can be ruled out. The clinical event, including an abnormal laboratory test result, occurs in a plausible time relationship to study procedures administration and cannot be explained by concurrent disease or other drugs or chemicals. The response to withdrawal of the study procedures should be clinically plausible. The event must be pharmacologically or phenomenologically definitive.
- **Possibly Related** – There is some evidence to suggest a causal relationship, and the influence of other factors is unlikely. The clinical event, including an abnormal laboratory test result, occurs within a reasonable time after administration of the study procedures, is unlikely to be attributed to concurrent disease or other drugs or chemicals, and follows a clinically reasonable response on withdrawal.
- **Not related** – A clinical event, including an abnormal laboratory test result, whose temporal relationship to study procedures administration makes a causal relationship improbable (e.g., the event did not occur within a reasonable time after administration of the study procedures) and in which other drugs or chemicals or underlying disease provides plausible explanations (e.g., the participant's clinical condition, other concomitant treatments).

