8.3.5 EVENT REPORTING

Adverse events and serious adverse events that will be tracked for this study are described in 8.4.1. Considering the nature of the study, we expect most of these events will be considered unrelated to the study procedures, including serious adverse events, like suicide attempts. If AEs/SAEs occur, the following procedure will be activated:

The research staff member who observes or is notified of an adverse event (e.g., significant distress during the baseline assessment) will notify the Principal Investigator (or his/her designee) on the same business day. The PI (or his/her designee) will complete an Adverse Event Form for each event and will determine if the event is an SAE. If the AE is determined to be an SAE, the Serious Adverse Event Form will be completed.

All reports will be made in writing to the NIMH DSMB representative, NIMH Program Official (PO), and sIRB. These reports should indicate that the monitoring entities (i.e., the PI and IRB, and/or DSMB) and appropriate regulatory entities (e.g., OHRP, FDA) have been notified in accordance with the approved monitoring plan and federal regulations. Reports will be submitted to the monitoring entity (e.g., NIH-DSMB) at least annually or on a schedule determined by the monitoring entity's policy. Monitoring entities may require more frequent reporting.

To local IRB and Sponsor

Any AE is reportable to the sIRB and local IRB within 5 business days *when it meets the following definition:*

Any harm experienced by a subject or other individual that, in the opinion of the investigator, is *unexpected AND at least probably related* to the research. (Note: A harm is *at least probably related* to the research if in the opinion of the investigator the research procedures more likely than not caused the harm.)

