8.4 UNANTICIPATED PROBLEMS

8.4.1 DEFINITION OF UNANTICIPATED PROBLEMS

This protocol uses the definition of Unanticipated Problems as defined by the Office for Human Research Protections (OHRP). OHRP considers unanticipated problems involving risks to

participants or others to include, in general, any incident, experience, or outcome that meets **all** of the following criteria:

- Unexpected in terms of nature, severity, or frequency given (a) the research procedures that are described in the protocol-related documents, such as the Institutional Review Board (IRB)-approved research protocol and informed consent document; and (b) the characteristics of the participant population being studied;
- Related or possibly related to participation in the research (“possibly related” means there is a reasonable possibility that the incident, experience, or outcome may have been caused by the procedures involved in the research); and
- Suggests that the research places participants or others at a greater risk of harm (including physical, psychological, economic, or social harm) than was previously known or recognized.

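### The causality grades in Section 8.3.3.2 leave no grade for worsening suicidality during treatment and are not mapped to the reporting rules that depend on relatedness

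*Combined protocol and SAP*

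**What the plan says.** Under Section 8.3.3.2 the treating counselor, the independent evaluator (IE), or both grade each adverse event, using timing and clinical judgment. There are three grades:

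- *Definitely Related*: "There is clear evidence to suggest a causal relationship, and other possible contributing factors can be ruled out".
- *Possibly Related*: "There is some evidence to suggest a causal relationship, and the influence of other factors is unlikely". The event must also follow within a reasonable time, and it must be one that "is unlikely to be attributed to concurrent disease or other drugs or chemicals".
- *Not related*: an event "whose temporal relationship to study procedures administration makes a causal relationship improbable", and for which another cause gives a plausible explanation. Both conditions are required.

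The rules that use relatedness are worded differently:

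- Section 8.3.5 requires a report to the sIRB and local IRB within 5 business days when a harm is unexpected and at least probably related. The second condition is met "if in the opinion of the investigator the research procedures more likely than not caused the harm".
- Section 8.4.1, on unanticipated problems, takes *possibly related* to mean that "there is a reasonable possibility that the incident, experience, or outcome may have been caused by the procedures involved in the research".
- Table 6 has two columns, related and not related to the intervention. Table 7 has a row for SAEs related to study participation. Neither says which grades count as related.

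Section 8.3.5 also states that "we expect most of these events will be considered unrelated to the study procedures", and it gives suicide attempts as an example.

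**The concern.** A causality scale should give every event a grade, above all the harm that the trial is most concerned with. Here that harm is worsening suicidality. Section 2.3.1 (Risk 1) accepts that treatment might cause it. Section 8.3.1 tracks a marked rise in ideation as an AE, Section 8.3.2 lists suicide attempts as SAEs, and Section 8.3.4 records deterioration of a baseline condition as an AE. Yet every student enters with moderate to severe ideation (Section 5.1), so an explanation other than treatment is nearly always at hand. Sessions are planned weekly (Section 6.1.6), so during active treatment the timing is usually compatible with a treatment effect.

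At stake are the prompt reporting and follow-up of events considered related, and the consistency of relatedness records. Two kinds of rater at four primary sites make these judgments, and Section 8.3.3.2 has no rule for disagreement between them.

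**Working it through.** No arithmetic applies beyond a count. The check crosses the two conditions on which the grades turn, then follows the result through each rule.

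**Step 1: does every event get a grade?**

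| Timing | Other explanation | Grade under 8.3.3.2 |
|---|---|---|
| Plausible | Unlikely or ruled out | *Possibly* or *Definitely* (if their remaining conditions hold) |
| Plausible | Plausible | None |
| Improbable | Plausible | *Not related* |
| Improbable | Not plausible | None |

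Two of the four combinations have no grade. Take a suicide attempt a few days after a session. *Definitely* fails because other factors cannot be excluded. *Possibly* fails because the underlying condition is a likely contributor. *Not related* fails because the timing does not make causation improbable. This is the second row.

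**Step 2: do the terms agree?**

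| Place | Term | Test |
|---|---|---|
| 8.3.3.2 | Possibly related | Other factors unlikely |
| 8.4.1 | Possibly related | Reasonable possibility of causation |
| 8.3.5 | At least probably related | More likely than not, in the investigator's opinion |
| Tables 6 and 7 | Related | Not defined by grade |

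The first two tests conflict. The attempt in Step 1 can be possibly related under 8.4.1 while failing the grade of the same name in 8.3.3.2. The third has no matching grade, and the fourth has no mapping.

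**Step 3: which actions change with the answer?**

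| Action | Depends on relatedness? |
|---|---|
| SAE to the program official within 3 business days (Table 7) | Yes, on relatedness alone; expected and unexpected SAEs are both included |
| Follow-up to resolution or stabilization, with a source comment if the event continues at 30 days (8.3.5) | Yes, on relatedness alone |
| sIRB and local IRB within 5 business days (8.3.5) | Yes, for unexpected events, by the investigator's own test |
| Non-fatal event to the DSMB immediately (Table 6) | Yes, for unexpected events |
| Unanticipated-problem report (8.4) | Yes, by its own test, for unexpected events that also suggest greater risk than was known |
| Deaths to the DSMB (Table 6) | No |
| SAEs to the DSMB within 72 business hours (8.3.5 text) | No |
| DSMB reports three times a year; annual IRB report (8.3.5) | No |

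The first two rows matter most. Under 8.3.3.3 an event consistent with natural progression is expected, so worsening suicidality would usually fall outside the rules limited to unexpected events. Those two rows still apply to it.

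**Step 4: a related conflict.** The 72-business-hour sentence covers SAEs without a causality condition. Table 6 puts non-fatal events that are not related, and expected related ones, on the tri-annual schedule. For a non-fatal SAE the two passages give different timing.

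**The case against.** A reader might infer that ungraded events will default to *Not related*, or that related harms will miss expedited IRB review. The documents do not support either reading. No text sets a default, and the typical event fails the *Not related* definition as well. The statement that most events will be considered unrelated is a forecast, not a grading rule. The sIRB rule carries its own definition and rests on the investigator's opinion, so a missing *probably* grade does not block it. The unanticipated-problem rule is likewise self-contained. These points stand.

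It can also be said that serious events reach the DSMB quickly whatever their grade: deaths immediately, SAEs within 72 business hours, and adverse event rates reviewed as they occur (Table 10). This stands for deaths. For non-fatal SAEs it stands only in part because of the conflict with Table 6, and the 72-hour sentence does not cover a non-serious rise in ideation.

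Raters are told to use clinical judgment, so they need not apply the definitions as a strict checklist. That is true, but judgment without an applicable category is where raters and sites can diverge.

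Finally, Section 9 plans no analysis by relatedness, and suicidality is compared between randomized strategies using assessments by blinded IEs. The treatment comparison is therefore not affected. The extra follow-up attached to related events is also uncertain: Section 8.3.4 sets limits of 7 days (AEs) and 30 days (SAEs) after the last intervention whatever the relationship, then says that events are followed to resolution or stabilization. Only the 30-day source comment is clearly confined to related events.

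**Conclusion.** The concern holds as a defect in the safety rules. The scale is not exhaustive, one of its terms conflicts with Section 8.4.1, and no text maps the grades to Section 8.3.5 or to Tables 6 and 7. Grading of worsening suicidality during active treatment is therefore undefined. Reporting of related SAEs to the program official, follow-up of related events, and the faster reporting of unexpected events may be applied inconsistently.

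The size is two ungraded combinations out of four, one of them the typical pattern for this trial's main harm. It cannot be turned into a number of events, because the documents give no event rates and do not define a reasonable time. The conclusion assumes that sessions are roughly weekly and that baseline suicidality is a plausible cause. It applies less during academic breaks, missed sessions and maintenance, and it does not arise in the same way for breach of confidentiality or coercion. The point merits correction before relatedness is tabulated, but it does not threaten the primary analysis.

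**What to change.** Rewrite the scale in Section 8.3.3.2 so that every event has one grade, using tests already in the protocol:

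- *Definitely*: other factors ruled out.
- *Probably*: more likely than not caused by study procedures (from 8.3.5).
- *Possibly*: a reasonable possibility, even if other factors could explain the event (from 8.4.1).
- *Not related*: no reasonable possibility.

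Add one sentence stating which grades count as related for Section 8.3.5, Section 8.4.1, Table 6 and Table 7. The wording of 8.3.5 points to *Probably* or higher and that of 8.4.1 to *Possibly* or higher. For the two tables the sponsor must choose, since the documents do not settle it. Reconcile the 72-business-hour SAE sentence with Table 6.

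The cost is a wording amendment and one more option on the event form. More events will be graded *Possibly*, and more may be reported faster. If Table 7 counts *Possibly* as related, this could include most suicidality SAEs during treatment going to the program official within 3 business days, so the workload should be weighed when the threshold is set. Any events already graded on the present scale would need regrading or separate tabulation.

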8.3.3.3 EXPECTEDNESS

The study team will be responsible for determining whether an adverse event (AE) is expected or unexpected. An AE will be considered unexpected if the nature, severity, or frequency of the event is not consistent with the risk information previously described for the study procedures.

- **Expected Adverse Event** – an adverse event that may be reasonably anticipated to occur because of the study procedure(s) or the natural progression of the subject's underlying disease, disorder, or condition.

- **Unexpected Adverse Event** – an adverse event that is not anticipated to occur because of the study procedure(s) or one that is not part of the natural progression of the subject's underlying disease, disorder, or condition.

8.3.4 TIME PERIOD AND FREQUENCY FOR EVENT ASSESSMENT AND FOLLOW-UP

The occurrence of an adverse event (AE) or serious adverse event (SAE) may come to the attention of study personnel during study visits and interviews of a participant presenting for care, or upon review by a study monitor.

As indicated in 8.4.1, AEs will be captured on the appropriate case report form (CRF). Information to be collected includes date and time the study team became aware of the event, event description, time of onset, study team's assessment of severity, relationship to study procedures, expectedness, time of resolution/stabilization of the event. AEs, as indicated in 8.4.1, occurring while on study will be documented appropriately regardless of relationship and will be followed until resolved or 7 days post-last intervention for all AEs or 30 days post-last intervention for all SAEs.

Any medical or psychiatric condition that is present at the time that the participant is screened will be considered as baseline and not reported as an AE. However, if the participant's condition deteriorates at any time during the study, it will be recorded as an AE.

Changes in the severity of an AE will be documented to allow an assessment of the duration of the event at each level of severity to be performed. Documentation of onset and duration of each episode will be maintained for AEs characterized as intermittent.

The study team will record events with start dates occurring any time after informed consent is obtained until 7 days (for AEs) or 30 days (for SAEs) post-last treatment visit. At each treatment visit, study counselors will document unsolicited AE/SAEs since the last therapy session discussed during that therapy session. At each study assessment visit, IEs will inquire about and document the occurrence of AE/SAEs since the last assessment. Events will be followed for outcome information until resolution or stabilization.

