Participant Duration: Total student participant duration is 26 weeks, which includes a 12-week follow-up assessment. Total student participant duration in active treatment can range from 4-14 academic weeks (not including campus holiday breaks or periods where students are ineligible for CCC services due to being out of state). Counselor participant duration will range from 1-2 years.

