6.1.6 ADMINISTRATION AND/OR DOSING

Treatment dosage for Stage 1 will consist of prescribed weekly sessions for up to 6 weeks for TAU or CAMS, followed by up to 8 weeks of CAMS or CC-DBT. It is assumed that weekly sessions align with typical CCCs. The counselor (interventionist) will be trained on CAMS and CC-DBT and will be evaluated for fidelity of implementation throughout the study. Length of time (e.g., student participant weeks in treatment) will be determined based on student participant responsiveness to their assigned treatment condition.

Except for the CC-DBT skills group and possibly other CCC therapy groups in the TAU condition, student participants will have no contact with other student participants, as this is an individualized treatment per each student participant.

Management of Student Participants in the Maintenance Phase. Student participants who are classified as responders during either stage 1 or stage 2 will end active study treatment and enter maintenance. Students may continue to receive CCC services during study maintenance. Students will continue to complete regularly scheduled IE assessments and remain in maintenance until the end of their study participation at 26 weeks. During the maintenance phase, the study team will contact students every four weeks. The four-week contact schedule will continue until their final assessment point. It is possible that students may experience a relapse in suicidality during the maintenance phase, which may be reported during the scheduled IE assessments, in response to a 4-week contact, or by the student spontaneously contacting a member of the CAMPUS trial clinical or research team. In these instances, students will be referred to their CCC for standard care. As noted elsewhere in this protocol (see section 6.5), treatments received outside of the study will be documented via the treatment history interview (THI).

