8.3.2 DEFINITION OF SERIOUS ADVERSE EVENTS

A Serious Adverse Event (SAE) is any adverse event occurring during the study or within 30 days of termination of the subject from the study that results in one or more of the following outcomes:

- Suicide death
- Non-suicide death
- Suicide attempt (not death) with non-zero intent to die
- Inpatient Hospitalization (specify below)
 - Suicidal ideation
 - Non-suicidal self-injury (NSSI)
 - Other mental health event (e.g., depression, homicidal ideation, anxiety)
 - Other non-mental health event (excludes scheduled hospitalizations for non-acute, unrelated cause such as an elective surgery)
- Emergency Department (ED) visit, not resulting in inpatient hospitalization (specify below)
 - Suicidal ideation
 - Non-suicidal self-injury (NSSI)
 - Other mental health event (e.g., depression, homicidal ideation, anxiety)

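### Section 8.3.4 ties AE and SAE recording to the last treatment visit, contradicting the study-based SAE definition in 8.3.2 and leaving 7.7 to 17.7 of the 26 on-study weeks under conflicting instructions

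*Combined protocol and SAP*

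**What the plan says.** Section 8.3.2 takes as an SAE "any adverse event occurring during the study or within 30 days of termination of the subject from the study" that leads to one of a list of outcomes. The list includes "Suicide attempt (not death) with non-zero intent to die", death by suicide, inpatient admission and mental-health emergency visits.

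Section 8.3.4 sets the onset window differently. Events are recorded if they start after consent and "until 7 days (for AEs) or 30 days (for SAEs) post-last treatment visit". Follow-up of an event has the same anchor: until resolved, or "7 days post-last intervention for all AEs or 30 days post-last intervention for all SAEs". Yet the same section has counselors note events at treatment visits and evaluators ask about and document events since the previous assessment at every assessment visit. The evaluator sentence has no end date.

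The end of treatment and the end of the study lie far apart. The Synopsis (1.1) states: "Total student participant duration is 26 weeks, which includes a 12-week follow-up assessment". It also says that "active treatment can range from 4-14 academic weeks". Under 6.1.6, responders leave study treatment and "remain in maintenance until the end of their study participation at 26 weeks". Section 4.5 places the end of study at the Week 26 assessment.

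**The concern.** Suicide attempts and psychiatric admissions are the central safety events of this trial. A student who responds in Stage 1 can finish treatment within 4 to 6 weeks and then spend most of the 26 weeks in maintenance. An attempt late in maintenance meets the SAE definition in 8.3.2 and should be documented under the evaluator sentence in 8.3.4. It falls outside the start-date sentence in the same section. A site that applies the start-date sentence literally could leave the event off the SAE form; a site that follows the other two provisions would file it. The protocol does not say which governs.

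The literal window also depends on what happens after randomisation: whether the student responds, how long Stage 2 lasts (1 to 8 weeks) and whether treatment is abandoned. The anchor itself is unclear too. Section 6.1.6 lets students use counseling center services during maintenance without saying whether such contacts count as treatment visits.

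**Working it through.** **Inputs**
- Participation of 26 weeks and active treatment of 4 to 14 academic weeks: Synopsis.
- Stage 1 of 4 to 6 weeks, Stage 2 of up to 8 weeks, last two evaluator assessments at Weeks 14 and 26: 4.2.
- Recording margin after the last treatment visit of 30 days (SAE) or 7 days (AE): 8.3.4.
- SAE definition margin after leaving the study of 30 days: 8.3.2.

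**Reproducing the plan's timeline.** Longest treatment is 6 + 8 = 14 weeks; with 12 weeks of follow-up, 14 + 12 = 26 weeks, as stated.

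**Formulas, in days from the start, with no academic-break pause**
- SAE recording closes at 7 × (last treatment week) + 30.
- On-study time outside the rule = 26 × 7 − closing day = 182 − closing day.
- The definition closes at 182 + 30 = day 212 (week 30.3) for a student who completes Week 26.

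| Last treatment visit | SAE recording closes | On-study time outside the rule | Part of 26 weeks | Gap to day 212 | Part of 212 days |
|---|---|---|---|---|---|
| Week 4 | 28 + 30 = day 58 (week 8.3) | 124 days (17.7 weeks) | 68% | 154 days | 73% |
| Week 6 | 42 + 30 = day 72 (week 10.3) | 110 days (15.7 weeks) | 60% | 140 days | 66% |
| Week 14 | 98 + 30 = day 128 (week 18.3) | 54 days (7.7 weeks) | 30% | 84 days | 40% |

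For AEs the 7-day margin closes the rule at days 35, 49 and 105 (weeks 5, 7 and 15). That leaves 147, 133 and 77 days, or 21, 19 and 11 weeks, outside it.

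Two checks on what this means:
- A week 15 event (day 105) is inside the SAE rule only if the last treatment visit was on or after day 105 − 30 = 75, about week 10.7. A week 22 event is outside it for every student on the planned schedule, because the latest closing point is week 18.3.
- Section 8.3.1 makes an evaluator rating of marked worsening at any assessment point an AE. Such a rating at Week 26 falls outside the 7-day rule even for the longest-treated student (closing at week 15), so the AE rule also conflicts with the AE definition.

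**Collection after the start-date rule closes.** Up to Week 26, the evaluators ask about events at their assessments (8.2, 8.3.4). The SITBI records suicide attempts (8.1, Table 1). The Treatment History Interview covers inpatient and emergency care at the end of Stage 2 and at follow-up (8.1). Students in maintenance are contacted every four weeks (6.1.6). From Week 26 to day 212 the definition still applies, but no contact is scheduled.

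**The case against.** The strongest reply is that the start-date sentence should not be read alone. Section 8.2 monitors AEs and SAEs at every treatment and assessment visit. Section 8.3.4 itself calls for documentation of events occurring on study and of deterioration at any time in the study. Under 8.3.5, staff who learn of an event notify the investigator the same business day, and the forms are then completed. None of these provisions has a treatment-based cut-off. This stands, and it rules out three stronger readings that a reader might infer.

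- *Late suicide attempts go unrecorded.* The documents do not show this. Up to Week 26 there are several routes by which an attempt would come to light. What is unsettled is whether it is filed as an SAE.
- *The DSMB receives an incomplete picture.* Section 8.3.5 sends all AEs and SAEs to the DSMB three times a year, and SAEs within 72 business hours of the site investigator's awareness. It also reports to the IRB events with onset after consent, with no end date. Reports would be incomplete only if sites applied the start-date rule literally and so did not file the event.
- *SAE counts are not comparable between strategies.* Section 9.3 plans no comparison of SAEs between strategies. The table above contrasts students by treatment length, which is not a strategy contrast. By Table 8 each responder belongs to both strategies that share a Stage 1 arm, and 4.2 assumes 50% response in both arms, so much of the difference would fall on all four strategies alike. Pilot Stage 1 attrition of 27% (CAMS) and 17% (TAU), not statistically different, means that equal windows are not assured. It does not establish a bias.

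The week 4 figure is also the extreme. Section 4.2 expects about half of students to respond in Stage 1, but 4.4 reports an average of 6 Stage 1 sessions in the feasibility study. The week 6 row (15.7 weeks, 60%) is therefore a fairer guide for a Stage 1 responder.

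What the reply does not remove is the contradiction. The start-date sentence is the only explicit onset window in 8.3.4, it disagrees with the SAE definition, and an outcome entry on the SITBI is not an SAE report.

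**Conclusion.** The recording rule in 8.3.4 is wrong as written and should be corrected. It contradicts 8.3.2 and the evaluator sentence beside it. On the planned schedule it leaves 7.7 to 17.7 of the 26 on-study weeks outside the SAE start-date rule, and 11 to 21 weeks outside the AE rule. Even a student treated for the full 14 weeks has on-study time outside both.

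Up to Week 26 this is a fault of conflicting instructions and of a literal window that varies with response and treatment length. Lost events, incomplete DSMB reports or unequal observation time between groups would follow only if the start-date rule were applied literally. The 30 days after Week 26 are a separate gap: the definition covers them and no scheduled contact does.

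The figures assume weekly timing without academic breaks and completion of Week 26. A break can move the last treatment visit later, and early departure brings the end of the definition forward; either narrows the gap for that student.

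**What to change.** In 8.3.4, replace the last-treatment-visit anchor with the study-based anchor of 8.3.2. Record AEs and SAEs with onset from consent to the end of study participation for every student, whatever the date of the last treatment visit. Align the follow-up sentence in 8.3.4 and the reporting text in 8.3.5 with this window, and summarise SAEs over it.

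For the 30 days after the Week 26 assessment, reconcile 8.3.2 and 8.3.4 in one of two ways. Either state that SAEs in that time are recorded when the team becomes aware of them, or end the definition at the last scheduled contact.

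In the same edit, correct the references in 8.3.4 and 8.3.5 that point to 8.4.1 for the tracked events. That section defines unanticipated problems; the event definitions are in 8.3.1 and 8.3.2.

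Cost: up to Week 26, a wording amendment and a note to sites, because evaluator visits already ask about events to that point. Existing visits do not cover the 30 days after Week 26. Recording on awareness adds little work, whereas active collection would need a new contact. If students have already passed through maintenance, a check of evaluator, SITBI and treatment-history entries against filed SAEs would show whether the literal rule has had any effect.
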